Healthcare providers of the patients in the SIGHT-guided intervention arm will receive alert messages, recommending consideration of genetic testing and referral to the genetics clinic. In contrast, providers of the patients in the standard care arm will not receive such alerts and will proceed with usual care practices. Patients with a score greater than equal to 0.30 and who have a scheduled visit at POD-C will be randomized in a 1:1 ratio to either the usual care or SIGHT-guided arm. Randomization will be stratified within the VUMC pediatric POD-C clinic. Patients will be excluded if they have already undergone Chromosomal Microarray testing at VUMC.

Objectives 7 Specific objectives or hypotheses

This study will evaluate the effectiveness of SIGHT as a clinical support system to prompt provider/patient discussion and shared decision making regarding the need for genetic testing in form of a chromosomal microarray. We seek to study if identifying patients with high SIGHT scores will decrease the duration of time to testing and increase diagnostic yield. SIGHT only relies on data already collected in routine clinical encounters and is calculated prior to a clinical visit at VUMC.

SIGHT does not replace clinical judgment in determining the necessity for genetic testing, but we seek to measure whether SIGHT increases the rates at which the important problem of elucidating the genetic etiology of disease is addressed. Our SIGHT-guided intervention group will be patients with high SIGHT scores where their provider receives a clinical communication recommending ordering of a genetic test and referral to the genetics clinic. Our comparison group will be patients with equivalently high SIGHT scores that receive usual care (i.e., do not receive a provider message). Patients will be from the POD-C pediatric primary care clinic at the Vanderbilt University Medical Center (VUMC) One Hundred Oaks location (OHO).

Trial design

8

Description of trial design including type of trial (eg, parallel group, crossover, factorial, single group), allocation ratio, and framework (eg, superiority, equivalence, noninferiority, exploratory)

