Analysis Metric: Time to event, measured from the initial patient visit to the time genetic testing is conducted.

Method of Aggregation: Median time in days

Specific Measurement Variable: Rates of genetic testing. **Analysis Metric:** Proportion of patients who received testing **Method of Aggregation:** Proportion of patients, presented as a percentage

Time Point: Assessed after one year to include enough time for patients to undergo testing through the usual course of care.

Specific Measurement Variable: Diagnosis via any genetic testing.

Analysis Metric: Proportion of patients diagnosed with a genetic disease following molecular testing or clinical evaluation. **Method of Aggregation:** Proportion of patients, presented as a percentage.

Time Point: Assessed after one year to include enough time for patients to undergo additional testing through usual care.

Specific Measurement Variable: Adherence to the SIGHT-prompted provider message.

Analysis Metric: Frequency of provider actions via referral to genetics and ordering a patient CMA following receipt of a SIGHT-prompted message.

Method of Aggregation: Proportion of instances where the provider follows the SIGHT recommendation.

Time Point: Information will be collected at the end of the study.

Participant timeline

- Time schedule of enrolment, interventions (including any run-ins and washouts), assessments, and visits for participants. A schematic diagram is highly recommended (see Figure)
 - 1. Enrollment Process: Eligibility Screening: Conducted at the initial patient visit. Consent Process: Following eligibility screening, informed consent will not be obtained as patients are following usual care.
 - **2. Interventions:** SIGHT-Prompted Provider Message: Initiated following screening for patients who meet the predefined risk threshold.
 - 3. Assessments: Baseline Assessment: Conducted during the initial visit, including collection of patient health data. Follow-up Assessments: Scheduled after initial visit to monitor the outcomes, such as number of patients receiving a diagnosis, time to genetic testing, and diagnostic yield.
 - 4. Visits: Initial Visit: SIGHT prompted provider message followed by review of referrals and documentation attributable to the initial patient visit. Subsequent Visits: Regular follow-ups as per usual pediatric care, during which recommendations and any genetic testing decisions are documented and assessed.

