The allocation will be done with a 1:1 ratio. This randomization process is designed to ensure that patients surpassing a previously defined threshold for predicted risk of needing genetic testing are randomly selected for the intervention group. A SIGHT-prompted provider message will be generated for patients in the intervention group, while patients in the control group will receive usual care without this prompted message.

Patients who exceed a predefined risk threshold and are scheduled for their first visit within a year will be eligible for randomization to the intervention group. An estimated 500 patients will be randomly selected to receive a SIGHT-prompted provider message as part of the intervention.

The comparator arm will consist of the random eligible patients who do not receive the intervention. These patients will not be a typical control group to avoid ethical concerns related to withholding potentially important care but will follow usual care and may still get genetic testing.

To maintain the integrity of the randomization process, the study will employ random allocation to intervention and comparator arms with the expectation of a 1:1 ratio over time.

This method of randomization aligns with ethical standards and the goal of the study to evaluate the effectiveness of the SIGHT intervention while ensuring that all patients receive the usual care appropriate to their clinical needs. Allocation concealment mechanism

Mechanism of implementing the allocation sequence (eg, central telephone; sequentially numbered, opaque, sealed envelopes), describing any steps to conceal the sequence until interventions are assigned.

The allocation sequence will be implemented using a secure, computerized system to ensure allocation concealment. This system will generate the allocation sequence and assign patients who surpass the predefined risk threshold to either the intervention or the comparator group.

The allocation system will maintain concealment by ensuring that randomization is not processed until a patient has been identified as eligible. This process occurs after the patient's eligibility is confirmed but before any intervention is assigned, to prevent selection bias and to maintain the integrity of the randomization process.

Implementation 16c

Who will generate the allocation sequence, who will enrol participants, and who will assign participants to interventions

Allocation Sequence Generation

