The allocation sequence will be generated by the study's data management team using a computer-based randomization function. Any pediatric patient scheduled for a visit in the POD-C pediatric primary care clinic at VUMC One Hundred Oaks (OHO) who meets or exceeds the predefined risk threshold will be flagged as eligible. These flagged patients will then be randomly assigned to either the intervention arm (SIGHT-prompted provider message) or the usual care arm (no provider message).

Participant Enrollment

Patients aged 1 to 20 years who have not previously undergone chromosomal microarray testing at VUMC will be automatically included in the randomization pool once they have a scheduled visit at the OHO clinic. As this study follows standard clinical care, patients themselves do not undergo a separate consent process for randomization. Instead, their providers will be informed of any SIGHT alerts only if the patient is randomized to receive them.

Assignment of Participants to Interventions

For those randomized to the intervention arm, a SIGHT-prompted provider message is generated within EPIC by a genetic counselor on the research team. This message indicates the patient's increased risk level and recommends considering a chromosomal microarray and referral to genetics. The provider maintains full discretion to act upon or dismiss this recommendation. By contrast, providers in the usual care arm receive no automated messages about SIGHT risk, and patients continue under routine care practices.

Concealment of Allocation

The randomization process is integrated into the workflow so that neither providers nor the study team can predict a patient's assignment prior to the system's automated allocation. This design ensures there is no foreknowledge of group assignment—preventing selection bias and preserving the trial's integrity.

Blinding (masking)

17a

Who will be blinded after assignment to interventions (eg, trial participants, care providers, outcome assessors, data analysts), and how

There will be no blinding of participants or physicians as patients and providers will follow usual care. Providers may dismiss the SIGHT – prompted provider message and not act on its recommendations at any time. No other intervention is planned. Patients would be unaware of the providers' decisions in that case unless the provider chooses independently to discuss the SIGHT score with them.

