A sample size re-estimation will be conducted after 250 patients have been randomized to account for uncertainty, and adherence rates for the initial test-referral rate used in the sample size calculation. An independent analyst, who will be blinded to the randomization assignment, will calculate the observed test-referral rate across all patients. This analysis will focus on updating the test-referral rate parameter to ensure the study is adequately powered. The updated test-referral rate will be used to reassess and, if necessary, adjust the total sample size to maintain the study's power at 80%. This process will ensure the trial remains robust and capable of detecting meaningful differences between the usual care and SIGHT-guided intervention arms.

17b If blinded, circumstances under which unblinding is permissible, and procedure for revealing a participant's allocated intervention during the trial

NA

Methods: Data collection, management, and analysis

Data collection methods

18a

Plans for assessment and collection of outcome, baseline, and other trial data, including any related processes to promote data quality (eg, duplicate measurements, training of assessors) and a description of study instruments (eg, questionnaires, laboratory tests) along with their reliability and validity, if known. Reference to where data collection forms can be found, if not in the protocol

The trial will utilize the SIGHT predictive model to generate a score for all POD-C patients. Data collection will include baseline and outcome data assessed via EHR data queries for internal genetic test orders in form of a CMA, referrals to pediatric genetics, and attributable dates. All queried metrics and additional metrics related to genetic testing results will be assessed and verified through chart review performed by a clinician (genetic counselor or geneticist) for the intervention and comparator arm for patients seen in the POD-C clinic. The validity and reliability of the SIGHT predictive model, as well as the data collection methods, have been ensured through pilot testing and chart review prior to study implementation. All data collected and related documentation will be available in the trial master file with data availability based upon institutional policy.

Plans to promote participant retention and complete followup, including list of any outcome data to be collected for participants who discontinue or deviate from intervention protocols

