c. Diagnosis via any test (molecular confirmation)	More patients will receive a diagnosis from molecular confirmation outside of firs tier testing via a CMA.	Number of patients flagged by SIGHT who receive a diagnosis via any test over one year vs controls [binary]	Chi-square test
d. Adherence to Intervention	Providers who Receive SIGHT prompts demonstrate higher adherence recommendations compared to controls	Proportion of eligible patients where providers ordered a CMA and place genetics referrals after receiving a prompt [binary]	Chi-square test; logistic regression adjusting for covariates

20b Methods for any additional analyses (eg, subgroup and adjusted analyses)

Subgroup analysis within demographic groups (sex, race, age) will be performed as described in the primary analysis but within each group or stratified by age.

Definition of analysis population relating to protocol nonadherence (eg, as randomised analysis), and any statistical methods to handle missing data (eg, multiple imputation)

Non-adherence and missing data for the SIGHT protocol are non-applicable in this context as patients will follow usual care. Patients who are lost to follow up or have no follow up care during the duration of the study will remain included in the analysis.

Methods: Monitoring

Data monitoring 21a

Composition of data monitoring committee (DMC); summary of its role and reporting structure; statement of whether it is independent from the sponsor and competing interests; and reference to where further details about its charter can be found, if not in the protocol. Alternatively, an explanation of why a DMC is not needed.

This study does not require a DMC as the protocol presents minimal risks to participants and adverse events or other problems are not anticipated. In the unlikely event that such events occur, unanticipated problems involving risks to subjects or others will be reported immediately to the PI and and within 7 days of the PI's notification of the event to the IRB.

21b Description of any interim analyses and stopping guidelines, including who will have access to these interim results and make the final decision to terminate the trial

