	Inclusion criteria: Inclusion criteria will consist of patients > 1 year old, < 20 years of age with a visit to POD-C pediatric primary care clinic at the Vanderbilt University Medical Center (VUMC) One Hundred Oaks location (OHO).			
	Exclusion criteria: Exclusion criteria will consist of patients who have been programmatically excluded due to having already received a chromosomal microarray at VUMC, and patients > 20 years of age.			
	Interventional			
Study type	Allocation: Randomized intervention model.			
Date of first enrolment	February 2025			
Target sample size	1000			
Recruitment status	Recruiting			
Primary outcome(s)	Number of cases diagnosed via a Chromosomal Microarray compared to the controls			

Information

Data category

Data category Info	Information		
Key secondary outcomes	 Time to patients receiving genetic testing Rate of genetic testing Satisfaction of physicians who received a SIGHT prompted provider message Number of patients receiving a diagnosis via any test (molecular confirmation), or a clinical diagnosis by a pediatric geneticist following the course of usual care. 		

*It is strongly recommend ed that this checklist be read in conjunction with the SPIRIT

2013 Explanation & Elaboration for important clarification on the items. Amendments to the protocol should be tracked and dated. The SPIRIT checklist is copyrighted by the SPIRIT Group under the Creative Commons "Attribution-NonCommercial-NoDerivs 3.0 Unported" license.

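### The any-diagnosis secondary outcome has three conflicting definitions, and the one in the registration table ties counting to a clinician whom the message recommends in one arm only

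*Protocol*

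**What the plan says.** Three places define the same secondary outcome:

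- **Item 12, Outcomes:** "Proportion of patients diagnosed with a genetic disease following molecular testing or clinical evaluation". It does not say who does the evaluating.
- **Item 20a, analysis table, row c:** "Number of patients flagged by SIGHT who receive a diagnosis via any test over one year vs controls [binary", tested by chi-square. The row label adds molecular confirmation and does not mention clinical diagnosis.
- **Registration data table, Key secondary outcomes:** a diagnosis by any test, "or a clinical diagnosis by a pediatric geneticist following the course of usual care".

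The message, according to item 16c, "recommends considering a chromosomal microarray and referral to genetics". It goes to one arm: item 6b says "providers of the patients in the standard care arm will not receive such alerts and will proceed with usual care practices". It is advice only, since "The provider maintains full discretion to act upon or dismiss this recommendation" (item 16c), and item 16a says that control patients "will follow usual care and may still get genetic testing".

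Item 18a collects data through "EHR data queries for internal genetic test orders in form of a CMA, referrals to pediatric genetics, and attributable dates". It then has a clinician check these metrics, and further ones on test results, by chart review in both arms. The eligibility criteria exclude only children with an earlier microarray at the centre. No section requires the counted diagnosis to be new. Item 17a states that physicians are not blinded.

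**The concern.** An outcome compared between arms should be found with the same probability in each arm when the truth is the same. The registration rule does not secure this for clinical diagnoses. It counts them only when a geneticist makes them, and referral to genetics is something the intervention is meant to increase; item 12 measures it as adherence.

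Take a child whose condition is recognised clinically by another specialist or the pediatrician, or was known before randomization. Without a geneticist visit the child scores zero. With one, the same child can score one. If more intervention children are referred, the counted rate rises although no child has gained a diagnosis. A secondary result offered as more genetic diagnoses would then partly measure referral.

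The three wordings also give different counts from the same records, so someone must choose among them. If that choice is made after outcomes are known, it can be steered by the results.

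**Working it through.** **Step 1: compare the rules for a child with a clinical diagnosis and no positive test.**

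| Source | Diagnosed by a geneticist | Diagnosed by another clinician |
|---|---|---|
| Item 12 | counts | wording silent; not excluded |
| Item 20a, row c | does not count | does not count |
| Registration table | counts | does not count |

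Only the registration rule expressly makes the count depend on who made the diagnosis.

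**Step 2: reproduce the plan's own figure.** Item 14 gives 0.09 × 0.09 = 0.81% for usual care and 80% power against 3.6% with 500 per arm. The sample-size formula gives 503 per arm with continuity correction and 434 without. Exact power at 500 per arm is 82.2% with the correction and 88.7% without. The plan's figure is reproduced with the correction.

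**Step 3: inputs for the size of the artefact.**

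- n = 500 per arm, and molecular diagnosis m = 0.81% in both arms (item 14; equal by construction, so there is no true effect).
- c = true share with a clinical diagnosis by some clinician, the same in both arms. **Assumed:** 2%, 5% or 10%.
- s = share seen by a geneticist. **Assumed:** 9% of controls, with item 14's usual-care testing rate as a stand-in, and 15% to 40% of the intervention arm. The upper value is 3.6% / 9% = 40%, the testing share that the target implies if yield stays at 9%.

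**Step 4: formulas.** The counted rate under the registration rule is m + s × c. For counts a and b in arms of 500:

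- Pearson X² = 1000(a − b)² / [(a + b)(1000 − a − b)].
- With continuity correction, |a − b| is replaced by |a − b| − 1.

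False significance is the exact binomial probability that X² exceeds 3.841 (level 0.05) or 6.635 (level 0.01). The level 0.01 is 0.05 / 5, taking the one primary and four secondary rows of the item 20a table as the Bonferroni family.

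Example: with s = 40% and c = 5%, control is 0.81% + 0.09 × 5% = 1.26% (6.3 of 500). Intervention is 0.81% + 0.40 × 5% = 2.81% (14.05 of 500).

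**Step 5: results.**

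| s, intervention | c | Control | Intervention | 0.05: Pearson / corrected | 0.01: Pearson |
|---|---|---|---|---|---|
| 15% | 5% | 1.26% | 1.56% | 6% / 3% | 1% |
| 25% | 5% | 1.26% | 2.06% | 16% / 10% | 5% |
| 40% | 2% | 0.99% | 1.61% | 12.5% / 8% | 3% |
| 40% | 5% | 1.26% | 2.81% | 42% / 31% | 19% |
| 40% | 10% | 1.71% | 4.81% | 81% / 75% | 59% |

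Allowing for children with both kinds of diagnosis changes the 40% rows at level 0.05 by less than one percentage point.

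**Step 6: check under the alternative rules.** If clinical diagnoses are left out (row c), or counted equally in both arms whoever made them, the counted rates are equal. Rejection then stays at or below about 5%; it is 4.4% at 0.81% per arm with the uncorrected test.

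**The case against.** The strongest reply is that the geneticist clause is not in the test the protocol specifies. Row c is a chi-square on test-based diagnosis, so the false-significance figures apply only if the registration wording governs. This stands, and it limits the point to a conflict of definitions with a possible bias.

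A reader might infer four stronger things that the documents do not support:

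- *That the message refers only the intervention arm.* It recommends referral, providers may dismiss it, and controls may be referred in usual care. The imbalance is one of degree.
- *That item 12 counts diagnoses by any clinician.* It is silent on this, and the registration wording could be read as filling the gap.
- *That control diagnoses made elsewhere are not sought.* Chart review covers both arms. Its stated scope does not expressly include diagnoses made on clinical grounds alone, but that is a gap in description only.
- *That the 42% or 81% is an estimate for this trial.* The 40% share comes from a scenario in which the intervention succeeds, while molecular yield is held at the usual-care rate. The 9% is a testing rate. The value of c appears nowhere. Clinically diagnosed controls may also reach genetics more often than other controls: with shares of 40% and 60%, the Pearson figure at 0.05 is 14% for c = 5% and 7% for c = 2%.

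Requiring a geneticist is also a defensible way to make a clinical diagnosis more certain, and a diagnosis that only the geneticist would have made is a real gain. Both are true. Neither removes the unequal counting of diagnoses made elsewhere or already known.

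**Conclusion.** The concern holds as a conflict among three definitions, one of which could create a difference between arms by the way diagnoses are found. It matters if the registration rule is used for the comparison. The row c test as written and the microarray primary outcome are untouched.

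The direction follows from the documents if referral rises in the intervention arm as intended. The size does not. It depends on the assumed clinical-diagnosis rate and on the assumed shares seen by genetics. It runs from close to nominal to large, and is smaller at a Bonferroni level. A lower significance level reduces false positives but leaves the estimated difference biased. The point should be corrected because the remedy is cheap, but it does not threaten the trial's main conclusion.

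**What to change.** Reconcile the three definitions before outcomes are assessed:

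1. Test outcome c on molecularly confirmed diagnosis by any test, as row c of the item 20a table already has it, and align item 12 and the registration table to that wording.
2. Report clinical diagnoses separately and descriptively. Count only those first recorded after randomization, whoever made them, and note who made each one.
3. State in item 18a that they are found by the same record search in both arms, for example from the Clarity billing codes that the nightly job in item 27 already processes, followed by the planned chart review.

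The cost is a wording change, a registry update and one further query. Two small downsides remain: diagnoses by non-geneticists are less certain, and coding by unblinded providers may still differ by arm. Both are reasons to keep these diagnoses out of the tested outcome.
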